The study will also determine whether successful treatment of PTSD symptoms improves the cardiac biomarkers proposed to underlie the excess CHD risk in PTSD.

Overview of the Study Approach. The proposed randomized controlled trial (RCT) uses an evidence-based intervention, CPT-C ([name] & Schnicke, 1992), as a tool to induce greater change in PTSD symptom severity compared to WP-CON. The use of a RCT design strengthens our results by controlling and quantifying variability and reducing potential confounding due to selection bias and will enable us to carry out our main goal which is to examine whether changes in PTSD symptom severity impact changes in CHD risk biomarkers. One hundred and twenty men

Figure 1. Pathophysiological Pathway to CHD in PTSD

and women (40-65 years of age) with current PTSD will be randomly assigned in a 2:1 ratio to receive CPT-C or to participate in a waiting period control (WP-CON) condition with minimal attention; CHD biomarkers will be evaluated at baseline and again after completion of CPT-C or after the WP-CON period (see Figure 2). Randomization will be stratified by variables known to be related to both PTSD and to CHD outcomes (gender, age [dichotomization point: 50 years], and comorbid Major Depressive disorder). During the treatment or waitlist phase of the study, PTSD symptoms will be measured every two weeks in each study arm in order to assess changes therein. The WP-CON group will receive minimal attention in the form of weekly telephone calls to assess current emotional state and to provide supportive, nondirective, brief counseling if participants report experiencing a crisis. All prerandomization baseline and post-intervention assessments of PTSD symptoms, psychosocial measures, health behaviors, and CHD biomarkers will be performed by assessors who are blinded to participants' randomization condition.

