General Analytic Strategies. We will examine all variables to determine if parametric distributional assumptions are valid (e.g., normality for the continuous variables). Variables not meeting approximate distributional assumptions will either be transformed or modeled using nonparametric methods. In addition, we will explore the variability and correlation structure of the CHD outcome variables and PTSD symptom severity. Evidence of imbalance in baseline demographic (age, gender, veteran/civilian status) or clinical (high blood pressure, diabetes, major depression) characteristics will be noted and discussed as to whether they are clinically significant and we will consider sensitivity analyses including these covariates in models (models described below separately for each aim), as recommended by the Committee for Proprietary Medicinal Products guidelines (Committee for Proprietary Medicinal Products, 2004). We will also minimize the imbalance on variables known to be related to the predictor and outcome variables by stratifying randomization by gender, age, and major depressive disorder. As the main goal of the aims for this study is to understand how changes in PTSD symptom severity impact changes in CHD markers, we will conduct both an intent-to-treat analysis where participants will be analyzed as part of the group to which they are randomized, regardless of intervention adherence, and a per-protocol or as-treated analysis to strengthen the evidence that the mechanism for the effects of CPT-C vs. control on CHD markers is through PTSD symptom severity changes.

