Expected Results. Because there are limited data and no studies evaluating the short-term effects of CPT-C on CHD biomarkers, HRV was selected as the primary outcome based on our limited pilot data; the other CHD markers will be secondary outcomes. We hypothesize that all CHD biomarkers will show improvement following CPT-C when compared to WP-CON, and the changes will be independent of changes in cardiovascular health risk behaviors, as defined by smoking, alcohol use, and low physical activity measured using the Stanford 7-day physical recall survey (Blair et al., 1985). It is likely that these cardiovascular health behaviors will remain constant or minimally change over the time period of the study.

Analytic strategy. The primary CHD risk biomarker, HRV, and secondary CHD risk biomarkers are continuous measures collected at baseline and 7-weeks (post-treatment) and therefore the same modeling strategy will be used for all CHD biomarker outcomes. To test the primary hypothesis of a CPT-C effect at post-treatment, we will use a general linear model that accounts for the correlation between participants' repeated outcome measurements over time with an unstructured covariance matrix (Verbeke & Molenberghs, 2000; Fitzmaurice, Laird, & Ware, 2004). The general form of the model is $Y_{it} = X_{it}\beta + \epsilon_{it}$, where Y_{it} is the CHD marker for subject i at time t=0 and 7 weeks. The predictors (X_{it}) in the model will include time and the CPT-C arm by time interaction. We will estimate the model parameters using the SAS procedure MIXED (SAS Version 9, Cary, NC), and contrasts will be written in the context of this model to test the difference of mean change in CHD markers between the two treatment arms at week 7. For improvement in precision, the model will also be adjusted for

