Approach. This RCT with repeated measurements of PTSD symptoms and CHD markers will provide a mechanism to evaluate the temporal relationship between the change in PTSD symptoms and the changes in ANS control mechanisms, endothelial function and inflammation. Using this temporal relationship, we will examine whether changes in PTSD symptoms mediate the effects of CPT-C on CHD markers.

Expected Results. We anticipate that the change in PTSD symptoms will mediate the relationship between CPT-C and CHD marker change, thereby identifying the role of reduction in PTSD symptoms as a mechanism for the improvement in CHD risk.

Analytic strategy. We propose to conduct mediation analyses using the more commonly known Baron and Kenny approach (Baron & Kenny, 1986) as well as the newer MacArthur approach (Kraemer, Kieser, Essex, & Kupler, 2008). By the MacArthur definition, the potential mediator must be during or post-treatment; therefore, the change in PTSD symptoms severity between week 0 and week 6 will be considered as a potential mediator. The outcome then will be participants' post-treatment change in CHD risk biomarkers, which will be determined at week 7. We will also explore the role of trajectories of change in PTSD symptom severity as a mediator of the post-treatment change in CHD risk biomarkers by deriving an individual-level summary measure of PTSD symptom change using the successive PTSD symptoms assessed at two week intervals. We will first fit a model to examine the relationship between the mediator (C) (i.e., change in PTSD symptoms during treatment) and

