A total of 120 male and female adults will be enrolled in the project. We will select for participation 50% men and 50% women and also 50% minorities. Based on our previous study recruitment efforts, we typically recruit at least 40% of the participants who are of minority status so a 50% inclusion rate should be attainable. We estimate that 215 potential participants will be screened, and 120 of these will be qualified to begin study procedures. Inclusion and exclusion criteria are as follows:

Participants must meet all inclusion criteria:

- Is between the ages of 40 and 65;
- Has current PTSD lasting at least three months, based on the Clinician Administered PTSD Scale (CAPS), DSM 5 version, with a CAPS total score of 25 or greater; and
- Will have been stable on any current psychiatric medications for four weeks prior to the Time 1 assessment.

Participants who meet **any** one of the exclusion criteria will be excluded:

- Is currently participating in evidence-based trauma focused therapy (e.g., CPT, prolonged exposure) for PTSD (current or past 6 months);
- Has current dementia or other memory loss condition, as indicated by self-report or as indicated by scores less than 20 on the Montreal Cognitive Assessment (MoCA);
- Has current psychotic spectrum disorder or bipolar disorder;
- Has current uncontrolled substance use disorder that would interfere with his/her ability to perform study procedures;
- Has a urine drug screen positive for cocaine and/or methamphetamine and reports regular use of that substance;
- Has severely impaired hearing or speech;
- Is pregnant;
- Has established heart disease, abnormal heart rhythm, cancer, or epilepsy
- Has HIV positive status with unstable disease status and/or unstable medication use;
- Has current exposure to ongoing trauma (e.g., physically abusive relationship);
- Has prominent suicidal or homicidal ideation (as assessed through a clinical interview);
- Has a serious/terminal illness or other health problem that would prohibit participation in the study;

- Has an inflammatory condition such as infection, fever, one-month history of accident or surgery, rheumatoid arthritis, lupus, or inflammatory bowel disease.
- Is unwilling to accept randomization; or
- Cannot agree to attend therapy sessions at least once per week.

Recruitment

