Cognitive Processing Therapy-Cognitive (CPT-C). CPT-C is a brief cognitive behavioral treatment for PTSD that has been found to produce a more rapid clinical improvement and lower dropout than the standard CPT ([name], Galovski et al., 2008). CPT-C is equally effective as the full version of CPT. Similar to the standard CPT, CPT-C consists of 2 hours of therapy each week for 6 weeks (i.e., two sessions). Any participant who cannot attend two sessions weekly will be allowed to participate in once session per week for a 12-week period. Study therapists will include two designated mental health providers trained in person by [name]. Initial didactic training (covering session by session procedures and core components of CPT-C) will last three days and be followed by training cases. Therapists will not be allowed to provide the intervention to research participants until they have demonstrated 100% competence and adherence with the required elements of all treatment sessions. Drs. [name] and [name] will provide biweekly supervision throughout the duration of the trial, conduct spot checks of videotaped sessions, and will provide as-needed individual consultation and an in-person refresher didactic training halfway through the trial. All therapy sessions will be recorded, and a random selection of 20% will be rated for fidelity checks during the study. In order to protect against drift, the frequency of fidelity checks will occur equally across the beginning, middle, and end of the intervention period. Two independent raters, Drs. [name] and [name], will code therapist treatment fidelity/adherence using the Cognitive Processing Therapy: Therapist Adherence and Competence Protocol Individual Version-Revised (Macdonald, Wiltsey-Stirman, Wachen, & [name], unpublished). Videos will be rated on the presence/absence of CPT-C elements, competence on these elements as well as proscribed elements.

Study therapy sessions will occur at DUMC South Clinics Building or at Traumatic Stress and Health Research Laboratory space at Hock Plaza. So that participants can park easily at Hock, we'd like to provide participants with parking passes in advance of their appointments. Because notification of randomization for therapy vs. waitlist control occurs by telephone, whenever possible, we will email (via Duke secured email) parking passes and directions to Hock to participants.

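### A 12-week CPT-C option is not carried into the timing of the outcome, the mediator or the 6-week control arm

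*Combined protocol and SAP*

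**What the plan says.** - **Length of CPT-C.** Interventions, CPT-C, describes two sessions a week for 6 weeks, then adds: "Any participant who cannot attend two sessions weekly will be allowed to participate in once session per week for a 12-week period". The exclusion list fits this, since it removes only a person who "Cannot agree to attend therapy sessions at least once per week".
- **Length of the wait.** WP-CON is 6 weeks in Significance and Specific Aims and in Interventions, and Subject Reimbursement pays for six control calls. Controls are offered CPT-C after their post-wait assessment.
- **When biomarkers are measured.** Overview of the Study Approach gives an event-based rule: "CHD biomarkers will be evaluated at baseline and again after completion of CPT-C or after the WP-CON period".
- **Primary analysis.** Aim 1, Analytic strategy, calls the biomarkers "continuous measures collected at baseline and 7-weeks (post-treatment", sets t at 0 and 7 weeks, and says the predictors "in the model will include time and the CPT-C arm by time interaction", with adjustment for the stratification factors. It has no elapsed-time term.
- **Mediation.** Aim 2, Analytic strategy, says "the change in PTSD symptoms severity between week 0 and week 6 will be considered as a potential mediator". The next sentence puts the outcome at week 7.
- **Symptom scores.** The Overview says "PTSD symptoms will be measured every two weeks in each study arm". Measures, PTSD and Psychiatric Evaluation, lists three PCL-5 time points during treatment or wait, plus the PCL-5 at each Holter recording and a post-intervention CAPS.

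**The concern.** The 12-week option does not appear to have been carried through to the measurement and analysis text, which is written for a 6-week course. An analyst handling a weekly attender would have to choose which rule to break, and that choice should not be made after seeing data.

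Aim 2 has most at stake. General Analytic Strategies says "the main goal of the aims for this study is to understand how changes in PTSD symptom severity impact changes in CHD markers". If symptom change is read halfway through therapy and biomarker change after all of it, the indirect effect is understated and the remainder moves into the direct effect. For Aim 1, any change in HRV unrelated to therapy between about weeks 7 and 13 would enter one arm only. No untreated control value is planned at that time, because controls may by then be receiving CPT-C.

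**Working it through.** **1. The plan's own figure.** Power Analysis gives SD 50, correlation 0.3, 80% power, alpha 0.05 (taken as two-sided) and 20% attrition from 80:40, leaving 64:32.
- SE = 50 × √[(1 − 0.3²)(1/64 + 1/32)] = 10.33 units.
- Detectable difference = (1.960 + 0.842) × 10.33 = 28.9 units, or 0.579 SD. Table 2 moves in steps of 0.05, so its 0.60 (30 units) is reproduced. The sample size is not in dispute.

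**2. Schedule.** Twelve sessions at one a week end at week 12. Keeping the plan's one-week gap between week 6 and week 7 gives:

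| | Twice-weekly CPT-C | Weekly CPT-C | WP-CON |
|---|---|---|---|
| Course or wait ends | week 6 | week 12 | week 6 |
| T2 if measured after completion | about week 7 | about week 13 | about week 7 |
| Sessions by week 6 | 12 of 12 | about 6 of 12 | – |
| Two-weekly PCL-5 scores over the course | 3 | 6 | 3 |

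The twice-weekly schedule satisfies every rule. The weekly schedule cannot satisfy both the after-completion rule and the week-7 outcome.

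**3. Completion rule governs: primary contrast.** Let f be the weekly share of CPT-C and d the mean untreated HRV drift over the extra six weeks. Neither is in the documents. Bias = f × d, and type I error = Φ(−1.96 + bias/10.33) + Φ(−1.96 − bias/10.33).

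| f | d (units) | Bias (units) | Share of 30 units | Type I error |
|---|---|---|---|---|
| 0.1 | 2 | 0.2 | 1% | 5.0% |
| 0.3 | 5 | 1.5 | 5% | 5.2% |
| 0.3 | 10 | 3.0 | 10% | 6.0% |
| 0.5 | 10 | 5.0 | 17% | 7.7% |

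**4. Completion rule for the outcome, literal week 0–6 for the mediator: Aim 2.** Assume full mediation. In weekly attenders, let m be the share of the CPT-C symptom effect present at week 6, r the correlation between individual week-6 and final change, g the CPT-C effect on symptoms in SD units, and k the ratio of the week-6 to the final within-group SD of change.
- γ1 ratio = 1 − f(1 − m)
- β2 ratio = [1/3 + (2/3)(1 − f + f·r·k)] / [1/3 + (2/3)(1 − f + f·k² + f(1 − f)(1 − m)²g²)]

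Worst corner at f = 0.3 (m = 0.5, r = 0.7, g = 1, k = 1): 0.85 × (0.940/1.035) = 0.772, which is 23% too small. Over m 0.5–0.75, r 0.7–0.9 and g 0.8–1.0, the product of coefficients is too small by:

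| f | k = 1 | k = 0.8 |
|---|---|---|
| 0.1 | 3–8% | 2–7% |
| 0.3 | 10–23% | 6–20% |
| 0.5 | 16–35% | 11–31% |

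**5. Week 7 governs.** Weekly attenders are then assessed after about 6 or 7 of 12 sessions. If, as an assumption, they show half the effect by then, the mean effect is 0.60 × (1 − f/2), and power = Φ(effect × 50/10.33 − 1.96). At f = 0, 0.10, 0.25 and 0.50 the effect is 0.60, 0.57, 0.525 and 0.45, and power is 82.8%, 78.8%, 72.0% and 58.7%.

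**The case against.** The strongest reply is that the mediation loss needs two clocks in adjacent sentences. Aim 2 puts the mediator at weeks 0–6 and the outcome at week 7. Read literally throughout, the two match; read nominally throughout, end-of-treatment symptoms are paired with a post-treatment outcome. This stands: step 4 applies only when the Aim 2 mediator window is combined with the Overview's outcome timing. But the literal reading measures weekly attenders mid-course, against the Overview, and the nominal reading leaves follow-up about six weeks longer in part of one arm.

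The text also leans towards nominal labels: Aim 1 glosses 7 weeks as post-treatment, and Aim 2 speaks of symptom change during treatment. That is a fair reading, but weeks 0 and 6 are also stated as an explicit rule. The requirement of eight weeks between blood draws does not settle it, because the baseline draw precedes randomization and T2 could still fall at week 7.

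End-of-course symptom data are largely planned already: PCL-5 at the T2 Holter, post-intervention CAPS, and paid symptom measures at therapy sessions. This stands, and it makes the repair cheap.

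Finally, Figure 2, which the Overview cites for timing, is not in the available text and may settle the visit schedule. One can say only that the available text does not reconcile these rules.

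A reader might infer that the primary result is materially biased, or that Aim 2 loses a fifth or more of its effect. The documents support neither. They give no weekly share and no HRV drift, and the weekly option is open only to people who cannot come twice a week.

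**Conclusion.** The inconsistency is real in the available text, and it is confined to CPT-C participants on the weekly schedule. Its size is unknown because their number is not stated.

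For the primary contrast the bias is probably negligible: the middle case moves type I error from 5.0% to 5.2%, and 7.7% requires half the CPT-C arm on the exception schedule together with a 10-unit untreated drift. For Aim 2, an attenuation of roughly 6–23% at an assumed 30% weekly share is illustrative. It depends on the assumed m, r, g and k, on full mediation, and on the mixed reading. If week 7 governs, the issue is mid-treatment assessment instead; the power figures in step 5 rest on an assumed half effect.

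Correction is worthwhile before analysis because the mediator window bears on the stated main goal and the repair costs little.

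**What to change.** 1. State one T2 rule: a fixed interval after the scheduled end of CPT-C or of the wait. Replace week 7 with post-treatment in the Aim 1 and Aim 2 analytic strategies.
2. In Aim 2, define the mediator as change from baseline to the end of the assigned course, using the last PTSD score before the T2 biomarkers. If the trajectory summary is used, continue the two-weekly PCL-5 through week 12 for weekly attenders (six scores, not three).
3. Record T1-to-T2 days and the CPT-C schedule, and report them by arm.

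Treat any elapsed-time or twice-weekly-only analysis as optional and descriptive; neither is precise enough to correct the result. At 30% weekly, an elapsed-time correction extrapolated from control change has an SE of 0.3 × (6/7) × 50√[2(1 − ρ)]/√32, which is 2.7 units at ρ = 0.3 and 2.0 at ρ = 0.6, against a middle-case bias of 1.5. A comparison limited to people who declared twice-weekly attendance before randomization would have a 95% half-width of 24.2 units if everyone had been asked (44.8:22.4), against 20.2 for the full sample. It would be 34.2 if only half could be asked. Enrollment had already begun, so the larger figure is the more realistic.

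**Cost:** wording changes, recording dates and schedule, up to three extra PCL-5 forms per weekly attender, and minor analysis work. No extra patients.

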Video recordings of therapy sessions will be made using a Duke-owned iPhone or iPad that is encrypted at levels compliant with FIPS 140-2 standards. The device to be used will be hardened such that only the video recording capability will remain. Video recordings will be moved from the device to the Duke shared server (file path above) as soon as possible after the recordings have been made, and will then be deleted from the mobile device. Any device that is not in use will be stored in a locked filing cabinet in [name] office. Video recordings will remain on the Duke shared drive until the fidelity raters are ready to evaluate them. Copies will then be moved to Box@Duke, where they can be viewed and evaluated by the raters. The recordings will be copied to an encrypted hard drive for permanent storage, and the copies on the Duke shared drive will be deleted. The encrypted hard drive will be stored in a locked file cabinet in [name] or [name] lab space at Duke South. Only the key personnel listed on the staff listing will have access to the encryption password and/or the hard drive.

Participants enrolled during the COVID-19 pandemic may be sent study equipment or study documents via FedEx. If that occurs, FedEx will be provided the name and address of the delivery recipient. No other information (including health information) will be included with the name and address.

Suicidal and/or Homicidal Ideation. The Traumatic Stress and Health Research Laboratory (TSHRL) has established standards of practice for the evaluation of risk of suicide and homicide. The policy includes a thorough risk assessment including evaluation of risk factors and protective factors associated with both suicide and homicide. Also included in the policy are differential recommendations for action based on determinations of low, moderate, or high risk. Any staff member conducting an interview in which moderate or high risk is determined will contact a senior staff person with clinical expertise in risk assessment [including the PI, co-investigator(s), and/or DUMC's Emergency Room]. Although we are not selecting PTSD patients based upon their level of depressive symptoms, our assessments may determine the presence of severe depression. If patients are acutely suicidal, they will be evaluated and appropriate referral or admission procedures will be initiated, and they will be dropped from further study. At several time points throughout the study, participants are reminded that they are asked to inform the study therapist, study coordinator, or study PI if they experience a psychiatric emergency such as homicidal or suicidal ideation. In addition, participants are provided the telephone

number of study staff who they can call in the case of psychiatric emergencies, including an after-hours contact number.

Post-Study Referrals for Participants. It is not unexpected that participants may complete the study with residual PTSD and/or major depressive disorder symptoms. Because participants complete the PTSD Checklist (PCL5) and the Beck Depression Inventory -II (BDI-II) at multiple time points, we will refer to these scores at the end of the study as a gauge of residual symptoms. We will provide referrals for continued treatment to anyone with a score of 38 or higher on the PCL5 and/or a BDI-II score of 20 or higher (i.e., moderate to severe depression range). Additionally, referrals will be provided to participants who self-report distress at symptoms of PTSD or depression (regardless of measure scores) and wish to continue with another form of treatment.

The TSHRL has developed patient educational materials regarding available resources, including portable resource cards for both veteran and civilian participants. Civilian resources may include local community mental health centers, local private mental health providers, Duke Adult Psychiatry Clinic, Duke's Psychology Clinic, and other resources such as emergency clinics and substance abuse treatment centers. Veteran resources include peer support (www.vtvettovet.org), local Vet Centers, and information about treatments available at various clinics at the DVAMC and local VA community-based outpatient clinics, including the PTSD Clinic, Mental Health Clinic, Mental Health Access Clinic, Psychiatric Emergency Clinic, and Women's Health Clinic. Where applicable and convenient to the participant, direct referral will be made in addition to providing resource cards.

Data Safety and Monitoring Plan. The individuals responsible for data safety and monitoring will be the PI, the co-Investigators, the study coordinator, and a Data Safety and Monitoring Board (DSMB). Mechanisms for monitoring and reporting of data safety and adverse events (AEs) will include ongoing participant contact via study personnel, to include check-ins about any adverse events, and weekly meetings between the PIs and study personnel.

Study staff members and the co-PI ([name]) will monitor ongoing clinical status throughout the project via direct interaction with the participants or through review of laboratory notes that will be completed at each visit by clinical and research staff. The PI will meet at least weekly with study personnel to discuss participants' reactions to the intervention, proper delivery of the intervention, and any adverse events or unanticipated problems. Regular meetings between investigators and the project manager will allow for ongoing progress reports, including the number of participants currently involved in the study groups, attrition rates, and scheduled data collection from participants, as well as notification and review of any AEs. Safety monitoring for AEs will be conducted in real time by the PI and/or project manager. The following information about adverse events will be collected: 1) the onset and resolution of the AE, 2) an assessment of the severity or intensity (use existing grading scales whenever possible), 3) an assessment of the relationship of the event to the study (definitely, probably, possibly or not related), and 4) action taken (e.g., none, referral to physician, start or increase concomitant medication). The PI will determine the severity of the event, will assign attribution to the event, and will monitor the event until its resolution. Any adverse events will be reported to the IRB in accordance with local guidelines. All research projects conducted at DUMC are

required to have yearly IRB review, including a safety review. Additionally, any changes to the project between review periods must be approved by the IRB prior to fielding.

Data Safety and Monitoring Board. This study will also utilize a Data Safety and Monitoring Board (DSMB) to enhance participant protection. Three consultants will serve as members of the Data and Safety Monitoring Board (DSMB) created for this project: 1) [name], University of North Carolina at Chapel Hill, will provide expertise in cardiology; 2) [name], University of North Carolina at Chapel Hill, will provide expertise in mental health; and 3) [name] [name], Dartmouth Institute for Health Policy and Clinical Practice, will provide expertise in biostatistics. The Data and Safety Monitoring Board (DSMB) will review adverse events and monitor the safety of participants and the quality and completeness of the accrued study data during regularly scheduled meetings. The DSMB will convene every year, but is consulted at any time in the event of study-related, unanticipated and/or serious adverse events. The DSMB performs the critical function of monitoring all studies for adverse events and determining whether a favorable risk-benefit ratio justifies continuation of a given study. The DSMB plays a complementary role to the Duke University IRB, which focuses mainly on the prospective review of study protocols (although the IRB may also be involved in halting a study in the face of serious, reportable adverse events). Decisions of the DSMB are made by majority vote, with the results of each vote and relevant discussion recorded in the meeting minutes (which, after circulation and emendation, are approved by each member).

Additional Information Regarding Data Analyses

Power Analysis. The sample size estimate of n=120 subjects (80 in the CPT-C arm and 40 in the control arm) is based on a 2:1 randomization and the AIM 1 comparison of HRV improvement between CPT-C and control arms at 6 weeks. For sample size calculations we used methods appropriate for ANCOVA type analyses (Borm, Fransen, & Lemmens, 2007), which are equivalent in terms of efficiency to our linear model for randomized trials (Fitzmaurice, Laird, & Ware, 2004). Quantities needed for this sample size calculation include the baseline standard deviation and the correlation between baseline and follow-up. As we have limited pilot data, we

Table 2. Effects size and mean differences of HRV detectable with 80% power in 120 randomized subjects.

Correlation	Standard	Effect Size	Mean
(rho)	Deviation	Difference	HRV
			difference
0.30	40	0.60	24.0
0.30	50	0.60	30.0
0.40	40	0.55	22.0
0.40	50	0.55	27.5
0.50	40	0.55	22.0
0.50	50	0.55	27.5
0.60	40	0.50	20.0
0.60	50	0.50	25.0

assumed a range of correlations between 0.3 and 0.6 and standard deviations (SD) of 40 and 50. **Table 2** presents effect size differences with 120 subjects. Using the most conservative assumptions, with 80% power, alpha=0.05, SD=50, rho=0.3, and 20% attrition rate by 7-weeks we can detect an effect size difference of 0.60 (Cohen, 1988), corresponding to a difference of 30 units in mean HRV levels at 7-weeks between CPT-C and control. For the AIM 2 mediation analysis, we will test that the effect of CPT-

C on CHD biomarkers is attributable to changes in PTSD severity. We determined detectable effect sizes for mediation based on empirical power estimates for the product-of-coefficient test (i.e., the product of γ_1 and β_2) given by Fritz and MacKinnon (2007). With 120 subjects and a type-I error of 0.05, we will have 80% power to detect medium to large effect size differences for each of the parameters individually (e.g, γ_1 and β_2) that are part of the product test.

Missing Data. Our plans for preventing and dealing with missing data follow the guidelines set forth by the National Research Council's Panel on Handling Missing Data in Clinical Trials. First, , we have numerous strategies in place to prevent attrition; based on prior experience with a similar design and population, we anticipate that we will have less than 20% attrition. Second, as recommended by the panel, we will conduct two general types of sensitivity analyses for our primary analysis. If the missing values are related to measured factors, such as treatment group or baseline comorbidities, then multiple imputation will be used to incorporate information for these auxiliary variables while still preserving a parsimonious main treatment effect model (Collins, Schafer, & Kam, 2001). As a first sensitivity analysis, we will construct a general, multivariate imputation model using all observed CHD markers, treatment group, and any covariates predictive of missingness (Olsen, Stechuchak, Edinger, Ulmer, & Woolson, 2012). The primary analysis models will then be fit to the multiply imputed data and the estimates and standard errors will be combined using appropriate combining rules. We acknowledge the possibility that data may be missing not at random and propose as a second sensitivity analysis to explore pattern-mixture models and the toolkit of methods recently advocated by O'Kelly and Ratitch (2014).

References

